8. OUTPUT PRESENTATIONS

Appendix 1 shows conventions for presentation of data in outputs. The shells document provided with this SAP describe the presentations for this study and therefore the format and content of the summary tables, figures, and listings to be provided by IQVIA Biostatistics.

9. DISPOSITION AND WITHDRAWALS

All patients who provide informed consent will be accounted for in this study. Cenduit will be the primary source for the randomization information.

9.1. DISPOSITION

Patient disposition and withdrawals will be presented for the RND set. Study medication and study withdrawals of patients will be presented by the date of the “End of Treatment/Disposition” page of the eCRF date of study withdrawal will be last available date within eCRF, the date of study medication withdrawal will be identified from End of Treatment page of the eCRF.

The number of study withdrawals and study medication withdrawals over the study will be summarized by treatment group and analyzed and presented through Kaplan-Meier plot using log-rank test, as described in section 16.3.3 of the SAP. Time to study medication discontinuation by subgroups of actual background medication strata and actual smoking strata will be presented through Kaplan-Meier plot.

Reasons for exclusion from each analysis set, as well as patients not meeting eligibility and randomization criteria will be presented for the ENR set with patients classified according to the randomized treatment. Patients not randomized will be presented in a separate category.

9.1.1. DERIVATIONS

Study day of early study medication discontinuation = Last day of study medication intake - First day of study medication intake + 1.

Study day of early study discontinuation = Last day in the study - First day of study medication intake + 1.

Visit for discontinuation will be presented using four subgroups (Not treated, \geq day 1 and \leq

week 6, > week 6 and \leq week 12 and > week 12 and \leq week 24), using the corresponding visit day windowing:

- week 6 = study day 53
- week 12 = study day 95
- week 24 = study day 179

9.2. PROTOCOL DEVIATIONS

PDs will be defined in the BDR report and the list will be finalized before the DBL.

9.3. EVALUATION INCLUDING EXCLUDED SITES

Site [REDACTED] was removed from the Randomized set. As a check of this exclusion, the patient disposition will be performed in the Extended Randomized set.

10. DEMOGRAPHIC AND OTHER BASELINE CHARACTERISTICS

Demographic data and other baseline characteristics will be presented for the RND. If there is a difference in patients between RND and mITT population, then demographic data and other baseline characteristics will also be presented for mITT.

[figure not shown]
Demographic data and other baseline characteristics will also be presented by subgroups of actual background medication strata and actual smoking strata for mITT.

No statistical testing is planned to be carried out for demographic or other baseline characteristics. The following demographic and other baseline characteristics will be reported for this study:

- Age (years)
- Age-class (years) (<65, \geq 65)
- Gender at birth
- Ethnicity (Hispanic or Latino, Not Hispanic or Latino (subgroup for rest of categories), Not Reported)
- Race
- Country
- Weight (kg)
- Height (cm)
- BMI (kg/m^2)
- FEV₁ reversibility at screening (yes, no)
- Modified Medical Research Council (mMRC) questionnaire score

Document: ...Verona_Pharma\RPL554\GZA93254\Biostatistics\Documentation\SAP\Verona CO-302 SAP FINAL v1.0_20220725

Author:

FINAL v1.0

25JUL2022

Template No.: C

Effective Date:

- Pre- and post-bronchodilator FEV₁ (both in liters and in percentage of predicted normal)
- Post-bronchodilator FEV₁/forced vital capacity (FVC)
- Time since initial diagnosis of COPD (years)
- Background medication strata [yes (subgroup for yes: LAMA, LAMA/ICS, LABA, LABA/ICS), no] –actual
- Known to have Chronic Bronchitis (yes, no)
- Known to have Emphysema (yes, no)
- Smoking strata (current (also includes stopped less than 6 months), former – stopped greater than 6 months ago) –actual recorded in the eCRF
- Number of cigarettes per day, Number of years smoking, Number of Pack Years
- COPD severity based on post-bronchodilator FEV₁ (Moderate, Severe, Very severe)

10.1. DERIVATIONS

- BMI (kg/ m²) = weight (kg)/ height (m)²
- Time since initial diagnosis of COPD = (date of consent – date first diagnosed)/365.25
- Pack Years = Number of packs per day x number of years smoking

Reversibility status is calculated based on pre-bronchodilator and post-bronchodilator FEV₁ values taken at Screening. If patient has increase of ≥12% and ≥200mL then patient is reversible, else patient is non-reversible.

Age (years) collected in the eCRF will be used for the analysis.

Pack Years is automatically calculated in the eCRF and this value will be used in the summaries.

COPD severity will be derived as follows based on post-bronchodilator screening spirometry:

- Mild: post-bronchodilator FEV₁ ≥ 80% predicted
- Moderate: 50% ≤ post-bronchodilator FEV₁ < 80% predicted
- Severe: 30% ≤ post-bronchodilator FEV₁ < 50% predicted
- Very severe: post-bronchodilator FEV₁ < 30% predicted

10.2. EVALUATION INCLUDING EXCLUDED SITES

As a check of the exclusion of site [REDACTED] from mITT, the demography and baseline disease characteristics will be performed in the mITT Extended.

•

11. SURGICAL AND MEDICAL HISTORY

Surgical and Medical History information will be presented for the SAF set.

- Surgical History will be coded using the Medical Dictionary for Regulatory Activities (MedDRA) central coding dictionary. The version of MedDRA to be used will be specified prior to database lock. Data captured on the “Surgical Procedure History” page of the eCRF will be presented by System Organ Class (SOC) and Preferred Term (PT) for each treatment group.
- Medical History will be coded using MedDRA central coding dictionary. The version of MedDRA to be used will be specified prior to database lock.
 - Medical History conditions, captured on the “Medical History” page of the eCRF, are defined as those conditions which stop prior to or at Screening visit and will be presented by SOC and PT for each treatment group.

12. CONCOMITANT ILLNESSES

Concomitant illnesses will be presented for the SAF set.

- Concomitant Illnesses will be coded using MedDRA central coding dictionary. The version of MedDRA to be used will be specified prior to database lock.
 - Concomitant Illnesses, captured on the “Medical History” page of the eCRF, are conditions which started prior to the first treatment dose and are ongoing at the date of first treatment dose, and will be presented by SOC and PT for each treatment group.
 -

13. MEDICATIONS

Prior, prior concomitant and concomitant medications will be presented separately for the SAF set and coded using the World Health Organization (WHO) drug code and summarized by Anatomical Therapeutic Clinical Classification System (ATC) levels 1, levels 2 and 4.

Possible therapeutic subgroups include ICS, LABA, LAMA, corticosteroids, short-acting B2 agonist, short-acting anti-muscarinic and combinations specified below, which are defined in a separate spreadsheet provided by the medical data reviewer. Combinations to be analyzed:

1. Oral or intravenous (IV) Corticosteroids
2. Oral or IV Corticosteroid & Other combinations
3. LAMA
4. LAMA/LABA

5. LAMA & OTHER COMBINATIONS
6. LABA
7. LABA & Other combinations
8. ICS/LAMA/LABA or ICS/LABA/LAMA
9. ICS/LAMA
10. ICS/LABA
11. ICS & Other Combinations
12. SABA/Short-Acting Anti-Muscarinic
13. SABA
14. SABA & other combinations
15. SABA/ICS
16. SABA/ Corticosteroid
17. Short-Acting Anti-Muscarinic

See APPENDIX 2 for handling of partial dates for medications, in the case where it is not possible to define a medication as prior, concomitant, or post treatment, the medication will be classified by the worst case; i.e. concomitant.

- ‘Prior’ medications are medications which started prior to the first dose of study medication and stopped prior to the first dose of study medication.
- ‘Prior Concomitant’ medications are medications which started prior to the first dose of study medication and ended on or after the date of first dose of study medication or were ongoing at the end of the study.
- ‘Concomitant’ medications are medications which:
 - started on or after the first dose of study medication and started no later than last day of study medication intake,
 - AND ended on or after the date of first dose of study medication or were ongoing at the end of the study.
- ‘Post’ medications are medications which started from the day after the last dose of study medication.

Prior, prior concomitant and concomitant COPD medications will be presented separately for the SAF set. COPD medications are those provided by medical review and will be presented as preferred term and ATC levels 1, levels 2 and 4.

Data captured on the “Concomitant Medications” page of the eCRF will be presented for each treatment group. Patients with multiple medications within an ATC/ therapeutic subgroup will only be counted once for that level.

Oxygen therapy and CPAP will be listed separately to other medications. Oxygen therapy is defined by ATC code: “V03AN” and route is not Oral; CPAP is defined by ATC code: “R07AX” and route is not Oral.

14. STUDY MEDICATION EXPOSURE

Exposure to study medication in days will be presented for the SAF set.

The dates of first dose of study medication administration will be taken from the “Drug Exposure” page of the eCRF (Day 1). The date of last dose of study medication administration will be taken as the latest date among all from the “Drug Exposure” and “Drug Exposure – Evening Blinded Study Medication Clinic Dosing” pages of the eCRF.

If no drug exposure were made at last visit and the dispensed drug supply was insufficient to cover use up to last visit, the last exposure day will be set to the day the drug supply should have been empty if patient had been compliant to twice daily regimen.

Interruptions and compliance are not taken into account for duration of exposure.

Study medication exposure will be presented using summary statistics by total number of days, and using frequency counts by subgroups: 1-42 days, 43-84 days, 85-126 days, 127-168 days and >168 days.

14.1. DERIVATIONS

Duration of exposure (days) = date of last study medication administration – date of first study medication administration + 1.

15. COMPLIANCE

Compliance to study medication based on dispensed and returned unused ampules and secondarily based on e-Diary entries will be presented for the SAF set.

Compliance will be presented using summary statistics by time intervals (Day 1 to Week12, Weeks 12-24 and full study length), as well as using frequency counts by subgroups: <50%, 50-70%, 70-80%, 80-90%, 90-100% and >100%.

15.1. STUDY MEDICATION COMPLIANCE

Study medication compliance will be summarized by treatment group in 2 ways:

- The number of ampules dispensed and unused returned will be taken from “Drug Accountability” page of the eCRF.
- Drug intake as recorded in the e-diary.

Patient is non-compliant, for study medication intake collected through the number of ampules dispensed/returned, if identified as taking less than or equal to 70% of blinded study medication during the period Day 1 to Week 12, or less than or equal to 50% over the study (Day 1 to Week 24). Calculations will not include time after treatment withdrawal.

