6.6 Blinded Study Medication Compliance

The prescribed dosage, timing, and mode of administration may not be changed. Any departures from the intended regimen must be recorded in the eCRFs.

At each visit, prior to dispensing blinded study medication, previously dispensed unused blinded study medication (ie, unopened or unused blinded study medication in taped foil pouches) will be retrieved by the unblinded site staff member and compliance assessed. Patients exhibiting poor compliance as assessed by the number of ampule/foil pouch counts dispensed and returned should be counseled on the importance of good compliance to the study dosing regimen and this counseling should be documented in the patient source document.

Noncompliance is defined as taking less than 70% of blinded study medication during any evaluation period (visit to visit).

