9.4.3 Other Analyses

The patient flow including total number of screened patients, number of randomized patients, completers, withdrawn patients (including reason for withdrawal) and patients

included in each of the analysis sets will be summarized by treatment group and for the total.

The number of patients with major protocol deviations will be summarized by category of violation and by treatment group including subset of major protocol deviation leading to exclusion from the per-protocol set.

Demographic and baseline characteristics will be summarized using descriptive statistics for each treatment group and for the total number of randomized patients. Medical history will be coded using MedDRA and summarized by system organ class and preferred term for each treatment group. Prior medications will denote medications used prior to first dose of study drug independent of if stopped at randomization or not. Concomitant medications will denote medications started prior to but continuing after randomization or medications with a start date at or after the randomization date. Prior and concomitant medications will be summarized separately by Anatomical Therapeutic Chemical (ATC) levels 2 and 4.

Compliance to blinded study medication will be computed based on the number of ampules/foil pouch count dispensed and returned. Non-compliance will be defined as a compliance value less than 70% over the full study period. Secondly, compliance will also be computed based on recording of study drug intake in the diary.

The impact of COVID-19 on the study participation of all patients will be captured on a separate eCRF page and include items such as attendance at in-clinic study visits. Details of presentation will be outlined in the Statistical Analysis Plan.

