3. STUDY DESIGN

3.1. GENERAL DESCRIPTION

This is a Phase III, multicenter, randomized, double-blind, parallel group, placebo-controlled study. A flow chart illustrating the key components of the study is provided in Figure 1:

Figure 1: Study Flow Chart

Approximately 800 patients with moderate to severe COPD aged 40 to 80 years (inclusive) will be stratified by two different factors: stable background maintenance long-acting muscarinic antagonist (LAMA) or long-acting beta-2 agonist (LABA) therapy use (yes or no) and cigarette smoking (current or former), then randomized 5:3 to receive ensifentrine (3 mg): placebo for 24 weeks. The background therapy strata will be capped at 50%. Up to 20% of patients are allowed to take inhaled corticosteroids during the study under certain provisions, as detailed in the sections 6.7.2 and 6.7.3 of the study protocol. Patients in the background maintenance LAMA or LABA therapy strata must withhold twice-daily maintenance LAMA or LABA (or LAMA/ICS or LABA/ICS) for 24 hours and once-daily maintenance LAMA or LABA (or LAMA/ICS or LABA/ICS) for 48 hours prior to initiation of any spirometry. All patients must withhold short-acting beta-2 agonist (SABA) rescue medication for at least 4 hours prior to initiation of any spirometry.

Patients are expected to take the study medication twice daily, administered via a standard jet nebulizer, during the study period. Schedule of in-clinic dosing can be found in section 1.4 of the study protocol.

3.2.SCHEDULE OF EVENTS

Schedule of activities can be found in section 1.3 of the study protocol.

3.3.CHANGES TO ANALYSIS FROM PROTOCOL

Changes to analysis from protocol include:

- “COPD severity” added as a subgroup analysis.
- Per-protocol population definition updated to exclude patients that discontinued study medication before study day 74.

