5.7. PER-PROTOCOL POPULATION

The per-protocol (PP) population will contain all patients in the mITT who did not discontinue the study medication before study day 74, and did not experience any major/important PDs considered to have an impact on efficacy assessments involving lung function at week 12. Reasons for exclusion will be specified at a BDR meeting prior to DBL and may include violations of inclusion/exclusion criteria, violations of withdrawal criteria, incorrect randomization, use of prohibited medication, did not follow blinding procedures and non-compliance. Patients will be classified according to randomized treatment.

If protocol deviations in terms of dosing errors are detected post unblinding, these will lead to exclusion only if patient has received and used the opposite study drug compared to what was specified in the randomization and that this use occurred prior to week 12.

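### SAP 15.1 rewrites the protocol's non-compliance definition without declaring it, and the per-protocol set used for Week 24 endpoints can keep patients with very low intake in Weeks 12 to 24

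*SAP*

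**What the plan says.** **Protocol.** The analysis definition is in section 9.4.3: "Non-compliance will be defined as a compliance value less than 70% over the full study period". Section 6.6, on study conduct and counselling, applies the same percentage to each interval: "Noncompliance is defined as taking less than 70% of blinded study medication during any evaluation period (visit to visit".

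**SAP 15.1.** On ampule counts, either of two limbs makes a patient non-compliant. The first concerns the lead-up to the primary endpoint: "less than or equal to 70% of blinded study medication during the period Day 1 to Week 12". The second limb looks at the whole treatment period: "less than or equal to 50% over the study (Day 1 to Week 24". The section then leaves out the time after a patient stops treatment: "Calculations will not include time after treatment withdrawal".

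**SAP 3.3.** The list opens with "Changes to analysis from protocol include" and contains one change to the per-protocol definition: "Per-protocol population definition updated to exclude patients that discontinued study medication before study day 74". The compliance limit is not in the list.

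**Per-protocol set.** Protocol 9.3 and SAP 5.7 both name non-compliance as a possible reason for exclusion, to be settled at the blinded data review. SAP 5.7 limits exclusion to "major/important PDs considered to have an impact on efficacy assessments involving lung function at week 12".

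**Use of that set.** Protocol 9.4.1 plans per-protocol sensitivity analyses for the primary and key secondary endpoints, and SAP Table 2 marks the set for both primary and secondary endpoints. In the SAP 7.4 hierarchy, three of the six key secondary endpoints are at Week 24: E-RS total score, SGRQ total score and SGRQ responders. SAP 16.2.4 nevertheless says that the key secondary sensitivity analyses are done at Week 12.

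**The concern.** For the same quantity, ampule-count compliance over the full study, the limit moves from below 70% to 50% or below, with no reason given and no entry in the list of changes. A reader who relies on SAP 3.3 would not know that the definition differs from the protocol's.

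The change could matter through the per-protocol set. The full-study limb is the only one that reaches Weeks 12 to 24, the period leading up to the Week 24 symptom and quality-of-life endpoints. If patients who took little drug in that period remain in the set, the per-protocol analysis of those endpoints comes closer to repeating the mITT analysis than to testing it among patients who followed the regimen.

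**Working it through.** The plan gives no figure of its own on this point, so the check compares the definitions and puts ampule counts through them.

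**Inputs**
- Limits: protocol 9.4.3 and 6.6, and SAP 15.1, as above.
- Denominators from SAP 15.1.1: (visit date − first dispensing date + 1) × 2, less 1 for a period ending at Week 24.
- Assumption: a completer with full supply and visits on Days 1, 85 and 169.

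**Expected ampules**
- Day 1 to Week 12: 85 × 2 = 170.
- Day 1 to Week 24: 169 × 2 − 1 = 337.
- Remainder after Week 12: 337 − 170 = 167.

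**Least intake that still counts as compliant over the full study**
- Protocol 9.4.3: 0.70 × 337 = 235.9, so 236 ampules (70.0%).
- SAP 15.1, second limb: more than 0.50 × 337 = 168.5, so 169 ampules (50.1%).
- Difference: 236 − 169 = 67 ampules. With both visits moved to the same end of the ±10-day window, the difference is 63 (222 − 159, of 317) or 71 (250 − 179, of 357).

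**Three patients**

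| Patient | To Week 12 | After Week 12 | Overall | SAP 15.1 | Protocol 9.4.3 |
|---|---|---|---|---|---|
| A | 120/170 = 70.6% | 49/167 = 29.3% | 169/337 = 50.1% | compliant | non-compliant |
| B | 170/170 = 100% | 0/167 = 0% | 170/337 = 50.4% | compliant | non-compliant |
| C | 119/170 = 70.0% | 167/167 = 100% | 286/337 = 84.9% | non-compliant | compliant |

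Patient A misses 337 − 169 = 168 doses and is also non-compliant under protocol 6.6, because Week 12 to Week 24 is a single dispensing interval. Patient B is the extreme case and must not be recorded as having stopped treatment. With visits on Days 75 and 159, patient B would need 9 later ampules to pass (159 − 150). Patient C shows the opposite direction: the Week 12 limb excludes someone whom the full-study rule would accept.

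**From the definition to the per-protocol set.** Patient A can stay in for two separate reasons. SAP 15.1 does not call this patient non-compliant. Even if it did, SAP 5.7 asks about impact on Week 12 lung function, and a shortfall confined to Weeks 12 to 24 has none.

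**The case against.** The strongest reply has four parts.

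1. **The rule is not simply relaxed.** A reader who sees only the 50% figure might infer a plain loosening. The other limb of the same sentence is one that protocol 9.4.3 lacks, and patient C shows that it can be stricter. It also guards the period that matters for the primary endpoint. This stands.

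2. **The link to the per-protocol set is indirect.** Section 15 of the SAP reports compliance for the safety set, and SAP 5.7 does not refer to 15.1. Non-compliance is only a possible exclusion reason, and the deciding criteria are in a separate blinded data review plan. A reader might infer that patients missing about half their doses will stay in. The documents support only that they can. This stands.

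3. **The 50% limit is not the only route.** A patient who stops on Day 75 after perfect intake passes the Day 74 rule and has 100% compliance, since time after withdrawal is not counted. That leaves 169 − 75 = 94 of 169 days without drug, under a 70% limit as much as under 50%. It would therefore be wrong to infer that restoring 70% in SAP 15.1 alone cures the problem. This stands, and it shapes the fix.

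4. **The Week 24 per-protocol analysis may not be intended.** SAP 16.2.4 places these analyses at Week 12. Read literally, that would drop the Week 24 endpoints from the per-protocol plan, against protocol 9.4.1, with no such change listed in SAP 3.3. The conflict is a reason to correct the wording. It does not settle the matter in the SAP's favour.

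In further mitigation, analysis sets are fixed before unblinding, and section 15 of the SAP tabulates compliance for Weeks 12 to 24 with bands below 50% and from 50% to 70%. The extent of low intake will therefore be visible. Neither point declares the changed definition.

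**Conclusion.** The SAP replaces the protocol's compliance definition with a two-limb rule and does not list the change. The new rule is tighter than protocol 9.4.3 to Week 12 and looser over the full study, by 67 of 337 ampules for an on-schedule completer (63 to 71 across the visit window). Because SAP 5.7 ties exclusion to Week 12 lung function, patients with very low intake in Weeks 12 to 24 can remain in the per-protocol analyses of E-RS total, SGRQ total and SGRQ responders at Week 24.

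This rests on two assumptions: that the blinded data review uses the SAP 15.1 definition, and that the per-protocol analyses cover the Week 24 endpoints, as protocol 9.4.1 and SAP Table 2 indicate. The documents do not show how many patients fall between the limits.

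A reader might go further and infer that the primary result is weakened. The documents do not support that. The primary analysis uses the mITT population, the per-protocol analysis is a sensitivity analysis, and the Week 12 limb largely protects the primary endpoint there too. This is a minor point, worth correcting because the correction is cheap.

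**What to change.** 1. **SAP 3.3:** list the new compliance definition and give its reason.
2. **SAP 15.1 and 5.7:** keep the Week 12 limb for the per-protocol analysis of Week 12 endpoints.
3. **SAP 5.7:** for the per-protocol analysis of Week 24 endpoints, state that patients below the protocol's 70% full-study limit are excluded, and judge deviations by their impact at Week 24. Say in the same place how patients who stop treatment between Day 74 and Week 24 are classified, since the compliance percentage cannot identify them.
4. **SAP 16.2.4:** correct the timing statement so that the Week 24 key secondary endpoints are analysed at Week 24.

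The data are already collected, and full-study compliance is already summarized with a cut at 70%. The cost is a few lines of SAP text, one extra per-protocol flag set before unblinding, and a somewhat smaller Week 24 per-protocol set, by a number that the documents do not allow one to estimate.
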